The proposed study will employ 58 ND treatment-seeking smokers who will be randomly assigned to receive either 15-mg of sirolimus or placebo (group n's=29) immediately after the first of two smoking cue exposure sessions scheduled to occur on consecutive days. The first session will serve as a **Retrieval** session during which smoking (e.g., handling and lighting of a cigarette) cue exposure will elicit retrieval and reconsolidation of smoking-related memories; the second session will be a **Test** session to examine the potential modulatory role of sirolimus on the reconsolidation of memories putatively elicited during the retrieval session. Participants will be required to refrain from smoking the night before (bedtime) their first laboratory (i.e., Retrieval) session and will remain abstinent from smoking until the completion of the second laboratory (i.e., Test) session. It is posited that changes in reactivity during the test session will reflect medication effects on memory reconsolidation that occurred following the retrieval session. Measures of subjective responses (i.e., craving) and physiological reactivity (i.e., heart rate & skin conductance) will be obtained before, during and after cue presentations in both sessions. The durability of any observed treatment effects will be assessed in a **Follow-up** session performed 7-days following completion of the test session. Treatment effects on self-report measures of smoking behavior during the 7-days preceding the Follow-up session will also be assessed.

Primary specific aim and hypothesis:

Aim: Evaluate the effects of post-retrieval sirolimus vs. placebo on measures of craving and cue reactivity administered 1 day and 1 week following the medicated **Retrieval** session.

Hypothesis: Compared to placebo treated smokers, sirolimus-treated smokers will evidence less craving, emotion/arousal and physiological reactivity to smoking cues presented during the (a) **Test** session and (b) **Follow-up** session.

Secondary specific aim and hypothesis:

Aim: Evaluate the effects of post-retrieval sirolimus vs. placebo on smoking behavior occurring during the one-week follow-up period.

Hypothesis: Compared to placebo-treated controls, sirolimus-treated smokers will evidence changes in smoking behavior during follow-up as indicated on multiple measures including (i) mean cigarettes per day, (ii) days to first cigarette, (iii) percent days non-smoking during follow-up.

[figure not shown]

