Since most smoking relapse occurs in the first week of cessation, a pharmacological aid that decreases craving and cue reactivity may make the difference between successful self-regulation and cessation vs. failed self-regulation and relapse. Favorable outcomes from this study could lead to a new generation of treatment adjuncts that would be brief, easy to administer and cost effective. These treatments could also become a complementary treatment paradigm, operating synergistically with the current generation of pharmacotherapies

and/or cognitive behavioral treatment approaches to reduce cue-elicited craving in nicotine addicted smokers. Because smoking is a primary causal factor in lung and other cancers, this translational, treatment-focused project has the potential to significantly advance **cancer prevention and control**.

II. Background

A. Significance:

Conceptual Overview: The role of basic associative learning processes in addiction has been well established in both theory and research¹⁻⁸. In smokers, numerous pairings between smoking-related cues (e.g., pack of cigarettes) and the reinforcing effects of nicotine can result in cues acquiring the ability to elicit a range of conditioned responses, most notably craving and physiological arousal. Importantly, there is substantial evidence that craving is powerfully associated with smoking relapse⁹⁻¹⁵. One viable explanation for this association is that craving undermines the **self-regulatory processes** (e.g., impulse control, emotion regulation, distress tolerance¹⁶⁻¹⁸) necessary to initiate and maintain cessation. Consistent with this conceptualization are the findings of neuroimaging studies suggesting that failures to self-regulate may occur when connectivity between prefrontal control regions (e.g., lateral prefrontal cortex) and subcortical reward regions (e.g., ventral striatum) are diminished or otherwise impaired¹⁷. Given this conceptual model, there are at least two approaches by which impaired self-regulation could be treated: a) restore/strengthen prefrontal-subcortical connectivity (see Project

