We expect to recruit 58 participants, equally allocated to treatment and placebo groups during the active treatment phase of the study. While literature is lacking on studies of the proposed treatment, we used data from our previous and ongoing work to derive an estimated standard deviation of 2.1 for single-item craving rating. Using this estimate and fixing power at 80% and $\alpha=.05$, we can expect to detect a minimum mean craving rating difference between the two treatment groups of 1.7 with 25 participants randomized to each treatment group (n=50). Although some attrition is expected, the proposed study uses a participant compensation strategy (see below) that is designed to minimize attrition. This strategy was based on one used in our previous NIDA-funded study of treatment-seeking smokers⁵⁹. In this study, we found 5% attrition occurs between two contiguous laboratory sessions where abstinence was required and 15% attrition at 2-week follow-up. Extrapolating to the proposed study, we are confident that 29 participants randomized to each study group (n=58) will provide sufficient power to evaluate expected group differences in this proof of concept study.

V. Setting

The research team will be conducting the research at the Research Nexus and the Addictions Studies suite of MUSC. Both locations have individual rooms for privacy. The Research Nexus has a specific room set up for collecting skin conductance and heart rate from the participants while simultaneously allowing the research assistant to monitor them.

VI. Recruitment Methods

Participants will be primarily recruited using local media (e.g., print, online, radio), a recruitment strategy that has been very successful in our previous and ongoing studies of ND smokers. We may also elect to recruit from the Medical University of South Carolina's (MUSC) Center for Drug and Alcohol Programs (CDAP).

VII. Consent Process

The study PI, Co-I or other research staff will obtain informed consent. The informed consent form includes a detailed description of the study procedures, along with statements regarding participants' rights to withdraw from the procedure at any time without consequences. The informed consent form will be explained to participants in easy-to-understand language, and participants will be instructed to read the form carefully prior to

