signing it. Consent will be documented by the signature of the participant on the informed consent agreement, accompanied by the signature of the individual obtaining the consent.

VIII. Study Design/Methods

A. Screening and Diagnostic/Abstinence Assessment:

Screening. All participants will be screened in two parts. First through a phone screen followed by an in-person screening. The screenings are both detailed above in the “determining eligibility” section.

Smoking and Other Drug Abstinence Assessment. Participants will be required to remain abstinent from smoking beginning at bedtime on the night before the (first) **Retrieval** cue exposure session and remain abstinent through the completion of the (second) **Test** session. Participants failing to meet the CO criterion at the Retrieval session will be allowed to reschedule their participation one time; however, if a participant fails the abstinence assessment on the second day, they will be dropped from the study because abstinence violators would be different from abstainers (a) with respect to the reconditioning of the putative learning/memory processes under study, and (b) amount of time elapsing between the Retrieval and Test sessions. Lastly, there will be no abstinence requirement for the 7-day period between the Test and Follow-up sessions; however, participants will be required to abstain from smoking starting at bedtime the night before the **Follow-up** session.

Briefly, participants will be informed that their participation (and associated compensation) in any given laboratory session will necessitate that they provide a breath sample that conforms with a CO criterion of ≤ 10 ppm. The full schedule of compensation is described in section F below.

Additionally, abstinence from alcohol and other drug use prior to all laboratory sessions will be confirmed via expired breath alcohol (BAC) and urine drug screen (UDS), respectively. A positive test will result in rescheduling/termination as described above for smoking; however, participants may test positive for cannabis/marijuana and continue to participate.

B. Cue Reactivity Session Measures: (This team has extensive experience using all listed measures).

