The recently-updated labeling for sirolimus (dated 1/2018) includes warnings regarding health consequences associated with sirolimus use. These warnings include increased susceptibility to infection and possible development of lymphoma due to the medication's immunosuppressive properties. The warnings that are potentially applicable to this protocol also include hypersensitivity reactions, angioedema, impaired or delayed wound healing, increased risk of opportunistic infections, and embryo-fetal toxicity.

However, many of these health consequences were observed with regular sirolimus use rather than a one-time dose, as will be the case in this study. Participants who are not willing to use an effective form of birth control during the course of the study and for twelve weeks after will be excluded from participating given the risk of embryo-fetal toxicity. Female participants will be pregnancy tested twice (including once on the same day as medication administration) and immediately excluded if the result is positive in order to avoid the risk of embryo-fetal toxicity. Participants will receive a maximum of 15mg of sirolimus under medically supervised conditions

Medication Preparation & Administration. Sirolimus (15-mg) and placebo will be compounded, packaged and dispensed by the MUSC Investigational Drug Service (IDS). The IDS and study Statistician ([name]) will oversee the randomization procedures. Immediately after the cue exposure in the Retrieval session, Sirolimus or a matching placebo will be administered.

E. Laboratory Session Procedures:

Session Preparation. Abstinence will be assessed (see above **A, Abstinence Assessment**) at each laboratory session visit. If abstinence is confirmed, participants will be escorted to MUSC's CTRC waiting room where they will remain until the laboratory is ready for cue exposure administration (approximately noon). Next, they will be escorted to the laboratory where they will sit quietly/read in order to acclimate to the environment until the cue exposure procedures begin. Following the acclimation period, HR and SC sensors will be placed, sound-attenuating headphones will be fitted, and baseline measures of subjective and physiological measures will be collected (see GENERAL PROCEDURES TABLE below).

Retrieval session 1 procedure. The primary objective of this session is to elicit the retrieval of smoking-

GENERAL PROCEDURE TABLE	Measurement				
	Single-Item Craving	HR	SC	Mood Form	QSU

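### The drop rule for a failed abstinence check, most plausibly applied at Test after dosing, removes early lapsers from the secondary smoking outcomes; keeping them in smoking follow-up is a cheap improvement

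*Combined protocol and SAP*

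**What the plan says.** Section VIII.A has two rules for a failed abstinence check. A failure at Retrieval may be rescheduled once. For the other case, "if a participant fails the abstinence assessment on the second day, they will be dropped from the study". Two reasons are given: violators differ in reconditioning, and in the time between Retrieval and Test. Alcohol and drug tests, cannabis excepted, follow the same path: "A positive test will result in rescheduling/termination as described above for smoking". A carbon monoxide result within the limit is also a condition of taking part in any session: "their participation (and associated compensation) in any given laboratory session will necessitate that they provide a breath sample that conforms with a CO criterion".

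Section I puts Retrieval and Test on consecutive days. Dosing comes before Test: "Immediately after the cue exposure in the Retrieval session, Sirolimus or a matching placebo will be administered" (VIII.D). For the week after Test, "there will be no abstinence requirement for the 7-day period between the Test and Follow-up sessions" (VIII.A), apart from the night before Follow-up.

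The secondary outcomes are "i) mean cigarettes per day, (ii) days to first cigarette, (iii) percent days non-smoking during follow-up" (Section I). Under VIII.E the diary that feeds them is handed out when Test ends, and staff do a Timeline Follow-Back (TLFB) interview at Follow-up if the diary is missing. Section IX names models for these outcomes. It gives no analysis population and no handling of dropped participants.

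**The concern.** The rule ends participation altogether, not only the contribution to the Test craving comparison. The reconditioning argument can support limiting that comparison to abstainers. It does not support losing smoking data for a week in which the plan lets everyone smoke. Someone who smokes just after Test contributes outcome data; someone who smokes the evening before Test and fails the check contributes none.

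The exclusion comes after randomisation and is tied to the behaviour being measured. It may also depend on treatment: the plan expects sirolimus to lower craving (Section I) and holds that "there is substantial evidence that craving is powerfully associated with smoking relapse" (II.A). Section IX intends the smoking results to help size a larger study, so a distortion here would carry forward.

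**Working it through.** **Inputs.** From Section IV: 29 per arm (58 in all), SD 2.1, detectable difference 1.7 with 25 per arm, 80% power, alpha 0.05, and "we found 5% attrition occurs between two contiguous laboratory sessions where abstinence was required and 15% attrition at 2-week follow-up". That 5% covers all causes. The lapse rates, the craving-lapse correlation (rho) and lapsers' later smoking are not in the documents and are assumed below.

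**1. The plan's own figure.** For a two-sided t-test with 25 per arm, the noncentrality is 1.7 / (2.1 × √(2/25)) = 2.86. Power is 0.801 and the detectable difference at 80% power is 1.698, so the stated figure is reproduced. With all 29 per arm, power is 0.858.

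**2. Which session is meant.** Retrieval failure has its own rule. Both reasons for dropping presuppose a completed Retrieval, and Test is the second of two consecutive days. Test is therefore the better reading. The other reading is a rescheduled Retrieval attempt. The drop would then precede dosing, and the plan would say nothing about a failure at Test.

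**3. Data route.** On the Test reading, the participant is out before the diary is handed out and before the TLFB fallback. No planned contact supplies the secondary outcomes.

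**4. How many.** If every loss in the 5% were an abstinence failure, 58 × 0.05 = 2.9 people, and the chance of at least one is 1 − 0.95^58 = 0.95. At 2% the figures are 58 × 0.02 = 1.2 and 1 − 0.98^58 = 0.69.

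**5. Test craving.** Craving is normal with SD 2.1 and is 1.7 lower on sirolimus. A participant lapses when rho × standardised craving + √(1 − rho²) × noise exceeds a threshold set so that 5% of placebo participants lapse.

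| rho | Difference among abstainers | Power, 29 per arm randomised |
|---|---|---|
| 0.3 | 1.68 | 0.839 |
| 0.5 | 1.64 | 0.829 |
| 0.7 | 1.59 | 0.822 |

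At rho 0.5 the implied sirolimus lapse rate is about 2%. A harsher calibration sets 5% as the average over both arms (placebo 6.2% to 7.7%) and holds the SD at 2.1. The difference is then 1.67 to 1.55 and power 0.83 to 0.77. If sirolimus affects neither craving nor lapse, the expected difference stays at 0.

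**6. Percent days non-smoking.** Let p0 and p1 be the placebo and sirolimus lapse rates, d the difference among non-lapsers, and g the gap between placebo non-lapsers and lapsers. With no benefit among lapsers, the difference in all dosed participants is d(1 − p1) + (p0 − p1)g. Dropping lapsers shows d instead.

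- *Benefit hidden.* d = 0, lapse 5% against 2%, g = 20 to 60 points: 0.03 × 20 = 0.6 to 0.03 × 60 = 1.8 points are missed.
- *Benefit overstated.* Lapse 5% in both arms and d = 14.3 points (one day in seven): 14.3 × 0.95 = 13.6, so dropping overstates by 0.7.
- *Reversed.* Suppose the 3% whom sirolimus keeps from lapsing then smoke like lapsers. The all-dosed difference is 0, while the retained comparison shows −(0.03/0.98) × g = −0.6 to −1.8 points.

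For scale, an assumed SD of 30 to 40 points gives a standard error of SD × √(2/29) = 7.9 to 10.5 points.

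**7. Sensitivity only.** At 20% placebo lapse, the step 5 model gives a craving difference of 1.42 to 1.64 and power of 0.72 to 0.77. At 20% against 10% lapse with d = 0, the percent-days shift is 0.10 × 20 = 2 to 0.10 × 60 = 6 points. Nothing in the documents suggests rates this high.

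**The case against.** The best counter-argument is size. At the plan's 5%, the percent-days shift is at most about a quarter of a standard error, and the move from 25 to 29 per arm already absorbs some loss. Section VIII.G reports very high abstinence compliance in earlier work, so true lapses may be fewer. Section IV calls the study a proof of concept, and Section IX already concedes that only large differences in smoking are likely to be detected. All of this stands, and it limits the severity.

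A second argument is that retaining violators is not a clean reference. Days to first cigarette has no natural value for someone already smoking, and a person turned away at Test also misses that cue exposure. This stands too. It calls for a stated time origin and an abstainers-only supportive analysis, but it does not justify collecting no data. An analysis of all dosed participants by assigned group keeps the protection of randomisation.

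A reader might infer more than the documents support:

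- *The rule favours one arm.* Step 6 shows the sign changes with the assumptions.
- *The data are lost for good.* TLFB is retrospective and is used in Section III over three months, so a later contact could recover the week. The supportable statement is that none is planned for dropped participants.
- *Safety follow-up stops.* Section X follows events to resolution and Section XI plans a phone contact during follow-up. What ends is visit-based assessment.

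**Conclusion.** The point holds as a cheap improvement of minor to moderate severity. On the better reading of VIII.A, dosed participants who fail a check at Test leave the study, and their smoking outcomes go with them. The reason given for the rule does not reach those outcomes.

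The expected loss is about 3 of 58 or fewer. At the plan's attrition figure the effect on Test craving is small: power stays above 80% at 5% placebo lapse and falls to 0.77 only at the harshest corner of step 5. The effect on percent days non-smoking is a point or two under the assumed gaps.

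The conclusion rests on 'second day' meaning Test. If it means a second Retrieval attempt, the post-dosing exclusion is not stated, and what remains is the silence about failures at Test. The documents do not support saying that the primary comparison is invalid or that the secondary results would mislead in a known direction.

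**What to change.** 1. The sponsor defines 'second day'.
2. If it means Test, and in any case for a dosed participant who fails a check at Test, replace removal from the study with exclusion from the abstainers-only Test craving comparison. Still collect smoking data, by diary or a TLFB contact, and adverse events through the follow-up week.
3. Analyse cigarettes per day, percent days non-smoking and time to first cigarette in all randomised, dosed participants by assigned group, with an abstainers-only supportive analysis.
4. State the time origin for time to first cigarette and how smoking before Test is counted, with the alternative as a sensitivity analysis.
5. Report abstinence violations by arm.

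**Cost.** A wording change, a time-origin rule and one extra contact for about 3 people. There is a trade-off with the incentive: under VIII.G a participant dropped at Test appears to forgo 75 + 100 = 175 dollars, and any payment for follow-up reduces that stake by the same amount. The payment level is for the sponsor to decide.

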Test session 2 procedure. This session provides an opportunity to test the hypothesis that rapamycin will acutely attenuate craving and physiological reactivity to smoking cues. Test session 2 will be identical to session 1 with the following exceptions. First, no medication will be administered. Second, at the end of the session, participants will receive a smoking diary in which to record the occurrence of any smoking behavior over the week follow-up period (abstinence is not required during the week preceding Follow-up session). Finally, the experimenter will provide compensation and schedule the Follow-up cue reactivity session.

Follow-up session procedure. This session affords the opportunity to assess the maintenance of any effects observed in Test session 2 and the effects of treatment on smoking behavior. In the Follow-up session, participants will experience the same session preparation and Retrieval session 1 procedures as described above with the following exceptions. First, no medication will be administered. Second, smoking diary data will be collected (research staff will perform a TLFB assessment of smoking behavior if participants do not present with their smoking diary). Finally, debriefing will take place to address questions or concerns that participants may be experiencing (blinding will be maintained). Referral for additional cessation treatment will be provided.

F. Timeline:

Since we have ongoing studies with a variety of substance using populations, an active recruitment network and extensive experience using cue reactivity paradigms, we anticipate start up to occur in approximately 4-months. During this period, research staff will be hired and trained, the protocol will be IRB approved at MUSC, an IND application will be approved by the FDA, and laboratory procedures and database(s) will be established. We will actively recruit participants for 18 months and plan to allow two months for final data cleaning/reduction, analysis and manuscript preparation (albeit manuscript preparation will begin sooner). At a recruitment rate of approximately 2-3 participants per month, we should have no difficulty in completing the study in the two-year timeframe. With regard to recruitment milestones, we anticipate being able to recruit approximately 26 ND smokers in the 8-month recruitment period of the first year and the remaining 32 participants in the 10-month recruitment period of the 2nd year.

G. Participant Compensation:

The compensation strategy for this study is designed to (i) provide remuneration for participant time and effort, (ii) maintain adherence to laboratory session schedule, and (iii) minimize abstinence violation and participant attrition. We have used this compensation strategy in a previous study (noted above) involving treatment-seeking smokers and have had very high levels of compliance with smoking and other substance abstinence.

Participants will be compensated as follows: Screening and assessment = \$50.00; Lab sessions 1 & 2 (Retrieval and Test) = \$75.00 each; 1-week Follow-up session = \$100.00. Maximum compensation for participation is \$300.00.

IX. Data Management

Primary Hypothesis. Mixed effects models will be used to test the hypothesized group differences at the Test (acute effect) and 1-week Follow-up (maintenance effect) laboratory sessions. Models will be developed to additionally assess the effects of potential covariates (e.g., age) on the single item craving outcomes and possible effect modification (through interaction terms). Other self-report measures (e.g., QSU, affect ratings, etc.) and HR/SC measures will be analyzed in a similar manner. Additional measures of craving, such as Area Under the Curve (AUC) and/or maximum within-session decrement in craving may be considered as outcomes. It may also be of interest to fit a covariance pattern model, analyzing craving over time, while accounting for treatment and session (Retrieval, Test & Follow-up Sessions). Secondary Hypothesis. Treatment group differences on various indices of smoking behavior (time to first cigarette, % days abstinent, CPD) will be assessed using general linear regression models while controlling for potential covariates. Continuous outcomes (% days abstinent, CPD) will be analyzed using normal linear models while time to first cigarette will be assessed using time to event models for efficacy analysis (Log-rank, Cox PH Models). Binary outcomes will be assessed using Logistic regression models. While only large group differences are likely to be statistically detectable, analysis of smoking behavior is consistent with the interventional focus of this research and will provide efficacy estimates to inform sample size estimation for a larger study.

X. Provisions to Monitor the Data to Ensure the Safety of Subjects

Data and Safety Monitoring Board. A Data and Safety Monitoring Board (DSMB) will be created to ensure the safety of participants and the validity and integrity of data collected during the project. The board will consist of Drs. [name], [name] and [name], all board-certified addiction psychiatrists, and [name], R.N., MSN, the Director of the Regulatory Core for the CTRC. The board will meet as needed to review the adverse events related to the study, and recommendations for appropriate action to maintain a favorable safety profile will be made. The board will also ensure that all serious adverse events have been followed to resolution, and that the appropriate agencies (including the IRB and internal funding agency) have been informed of the event.

Adverse Event Monitoring

Adverse events will be monitored throughout the study and all events will be followed to resolution or stabilization. All serious adverse events will be collected and reported immediately to the IRB and the internal funding agency (Hollings). Serious adverse events related to rapamycin (sirolimus) will be reported to the FDA. A serious adverse event is one that meets any of the following criteria:

1. Fatal or life threatening
2. Requires or prolongs inpatient hospitalization
3. Results in persistent or significant disability/incapacity
4. Congenital anomaly
5. Medical event that may jeopardize the participant or require intervention to mitigate serious outcome
6. Cancer
7. Overdose
8. Results in the development of drug dependency or abuse.

XI. Risks to Subjects

Rapamycin (Sirolimus; Rapamune®) Dosage and Potential Side Effects. The decision to employ a 15 mg dose of rapamycin (sirolimus) in the proposed study was based on the following rationale. First, as noted in the main application, there was a dosing precedent established in the clinical literature. Specifically, the previously noted study by Suris et al, 2013 employed 15 mg of rapamycin to disrupt trauma-related memories in combat veterans. The study results suggested, in a subsample of non-Vietnam era veterans, that 15 mg of rapamycin vs. placebo administered in conjunction with trauma memory reactivation was associated with decreased PTSD symptomatology at a 1-month follow-up assessment. Importantly, they also documented that this dose was not associated with any adverse medical consequences or side effects.

In addition to the precedent set by the Suris et al study, there is strong animal and clinical pharmacokinetic (PK) and pharmacodynamic (PD) data to demonstrate the proposed dosing regimen will demonstrate clinically relevant outcomes. Results from a number of clinical PK studies demonstrate that sirolimus is rapidly absorbed after oral ingestion, with peak whole blood concentrations occurring 1.0 to 1.3 hours after administration¹⁻³

Additionally, sirolimus adequately crosses the blood brain barrier, with an estimated blood to brain ratio of 1:34. In a clinical PK study in health males, an 8-mg/m² one-time oral dose produced a whole blood C_{max} of 115.2 ng/mL at 1.0 hour after ingestion. This corresponds to an approximate peak brain concentration of 38.4 ng/mL⁶⁰. Additionally, the organ transplant animal and clinical data strongly support the proposed dosing strategy. Studies conducted in rats using sirolimus to prevent organ rejection utilized dosing ranges between 0.5 to 50 mg/kg per day⁵. However, maximum pharmacodynamic activity with sirolimus monotherapy in rat kidney and heart transplant models was demonstrated with a dose of 8 mg/kg intravenously. This dose correlated with a mean AUC_{0-24h} of 270 ± 12 µg/L*h⁶. By using the trapezoidal rule, the AUC_{0-∞} in rats for an 8 mg/kg dose would approximate 350 µg/L*h. This dose of sirolimus also demonstrated maximal lymphocyte protein kinase inhibition at 2 hours post-dose (i.e., maximal protein synthesis inhibition), with return of full function occurring at 12 to 24 hours post-dose. Therefore, based on the above noted literature, a one-time 15 mg dose should produce substantial protein kinase inhibition in the brain within 1-1.3 hours of administration, while also being well tolerated, with mild-transient side effects. The current clinical use of sirolimus in organ transplantation also supports using the 15 mg oral dose in this proposed study, as it is commonly given as a loading dose of 15 mg orally during the perioperative period⁶.

